- 2) Within 24 hours of an adverse event being identified, an Adverse Event Report form will be completed by the study staff member or supportive housing provider who identified the event. The report form will include date, description of the event, duration, severity, measures taken to ameliorate the adverse event, and disposition related information (e.g., time spent providing referrals and type of referral (e.g., mental health treatment, ER visit, etc.). The report form will be reviewed and signed by the immediate supervisor who will be responsible for ensuring that appropriate actions have been taken.
- 3) Once the PI becomes aware of an adverse event, he will, in consultation with the study physicians as necessary, assess the event to determine whether the adverse event was an unanticipated problem by evaluating 1) was it unexpected, and if so, 2) was it possibly related to study participation, and if so, 3) does it qualify as a serious adverse event or suggest that the research places subjects or others at greater risk of harm than previously recognized. In making this determination, the PI will consult with housing provider staff and the physician co-investigators on the study, as well as review any documentation or other sources to clarify the nature of the event and outcomes. The PI will report any events that meet the three criteria to the IRB as unanticipated problems within 1 week of the PI becoming aware of the event. The PI will consult with the investigative team, DSMB, and supportive housing provider to determine whether protocol changes are needed. The PI will maintain a log of all adverse events and present a summary report for the DSMB to review.
- 4) The investigative team and the DSMB will review all adverse event data every six months to determine if systematic trends exist among adverse event data to warrant changes to study protocols and procedures. Any proposed changes will be reviewed with staff at the study sites, and, if needed, external consultant (e. g., other senior investigators conducting federally-funded research on the physical health of people with SMI).

Approval for changes in study protocol or materials will then be obtained from the Columbia University IRB and other study site's IRB. After approval, the NIMH program official will be

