Conflict of Interest: DSMB members will be asked to disclose any conflicts of interest prior to DSMB meetings. No DSMB members will have any role on the study.

Charge of the Board: During the trial, the DSMB will assess the performance of overall study operations and any other relevant issues, as necessary. Specific items that will be reviewed by the DSMB include:

- Interim/cumulative data for evidence of study-related adverse events
- Data quality, completeness, and timeliness
- Adequacy of compliance with goals for recruitment and retention, including those related to the participation of women and minorities
- Adherence to the protocol

- Factors that might affect the study outcome or compromise the confidentiality of the trial data (such as protocol violations, unmasking, etc.)
- Interim analysis

Meeting Format: The meetings may include both open and closed sessions. In the open sessions, the PI and the Project Director presents and discusses information with the DSMB on study progress and adverse events. In closed sessions, the DSMB chairperson leads the meeting with the board members and without participation of the PI or study investigators to discuss any concerns with the progress of the study or with risks to participants. The need for closed meetings is at the discretion of the DSMB chair. Meetings may be conducted by teleconference at the request of Board members.

Frequency of Meetings: The first DSMB meeting will take place before the enrollment of the first participant in the effectiveness study. During the first DSMB meeting, a chair for the board will be selected. Then, the DSMB will meet once a year until the completion of the study. Additional meetings will be convened quickly if problems arise that require addressing between reviews. Ad hoc DSMB meetings may be requested by DSMB members, the Project Officer (PO), Columbia University IRB, or Principal Investigator (PI) at any time to discuss safety concerns.

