What is Monitored: The DSMB will evaluate the progress of the trial, recruitment rates, retention rates, adverse events, unanticipated problems, and other factors affecting safety or outcomes. The DSMB will review rates of adverse events in the study (in an unblinded manner if they wish) to evaluate any changes in participant risk. The PI, Project Director, and study statistician ([name]) will be available to the DSMB to provide summary data on recruitment, data quality, adverse events, and will provide requested data analyses. The DSMB also will review major proposed modifications to the study prior to their implementation.

Confidentiality: The DSMB will not have access to personally identifiable information of participants. DSMB members agree not to disclose the results of the data except as agreed by the PI. The report to the DSMB includes actual vs. projected recruitment rates (number screened, consents, randomized, etc.), summary of serious adverse events, and any modifications to the protocol.

Communication Plan: At the end of each DSMB meeting, the chair will provide the study leadership with written information concerning findings for the trial as a whole and any relevant recommendations related to continuing, changing, or terminating the trial. The chair will prepare a summary of the meeting along with any recommendations for changes to the protocol based on the meeting. The draft report will be reviewed and edited by all Board members prior to issuing the final report. This report will not include confidential information. The report should indicate whether the study should continue as originally designed, whether the study should be modified to protect patient safety or whether the study should be terminated. The PI will send the report to the Columbia University IRB, other study site's IRBs, and to the sponsoring NIH Institute.

13. Potential Benefits

The potential benefits to participants are direct (improved health and wellness) and indirect (helping to refine the appropriateness and promote the use of a promising group-based healthy lifestyle intervention). The study will test the effectiveness of Peer GLB to improve the physical health of culturally diverse consumers with serious mental illness who are overweight or obese receiving services at supportive housing agencies.

14. Alternatives

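### Does a yearly DSMB meeting schedule defeat the commitment to review adverse events every six months?

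*Combined protocol and SAP*

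**What the plan says.** All the relevant text is in section 12, Data and Safety Monitoring.

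- **Adverse Events, item 3:** "The PI will maintain a log of all adverse events and present a summary report for the DSMB to review". No date or frequency is attached to this report.
- **Adverse Events, item 4:** "The investigative team and the DSMB will review all adverse event data every six months". The purpose is to look for systematic trends that would justify changing the protocol. Proposed changes then go to site staff, to an external consultant if needed, and to the IRBs for approval.
- **Charge of the Board:** the board's items include "Interim/cumulative data for evidence of study-related adverse events".
- **Meeting Format:** "Meetings may be conducted by teleconference at the request of Board members".
- **Frequency of Meetings:** after a first meeting before enrollment, "Then, the DSMB will meet once a year until the completion of the study". It adds: "Additional meetings will be convened quickly if problems arise that require addressing between reviews". Board members, the project officer, the Columbia IRB or the PI may also request an ad hoc meeting on safety concerns at any time.
- **What is Monitored:** the PI, Project Director and statistician supply adverse event summaries and any analyses the board requests. The board may look at adverse event rates unblinded.
- **Communication Plan:** "At the end of each DSMB meeting, the chair will provide the study leadership with written information", followed by a report with a recommendation to continue, modify or stop. "The PI will send the report to the Columbia University IRB", to the other sites' IRBs and to the NIH institute.

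**The concern.** Item 4 is the step meant to pick up a pattern across events that no single report would reveal, and it asks for this twice a year. The meeting schedule provides one occasion a year, and the board's written findings are tied to meetings. A reader could conclude that every second review has no scheduled occasion, or takes place on paper without a recorded conclusion.

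At stake would be the timing of the independent look at safety. If only the yearly meeting took place, the gap between independent looks would be 12 months, as long as the intervention itself. Section 11 says the risk of low blood sugar in participants on antidiabetic medication is greatest early on, so a group that began just after a yearly meeting could nearly finish before the board next looked.

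The main outcome, its analysis and the trial's conclusions on weight loss are not affected on any reading.

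**Working it through.** The plan gives no figure to reproduce here. The check is a count of intervals and then a comparison of the provisions.

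**Inputs.** Review interval 6 months (Adverse Events, item 4). Meeting interval 12 months (Frequency of Meetings).

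**Count.**
- Committed reviews per year: 12/6 = 2.
- Scheduled meetings per year: 12/12 = 1.
- Share of committed reviews with no scheduled meeting: (2 − 1)/2 = 0.50.
- Over D years the counts are 2D reviews and D meetings. The available text does not give the trial's length. Assuming 2 to 5 years, that is 4 to 10 reviews against 2 to 5 meetings. The share stays at 0.50.

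**Delay, if the yearly meeting were the only look.** Suppose a trend is equally likely to start at any time in an interval of length T. The mean wait to the next look is T/2.
- Yearly: 12/2 = 6 months, at most 12.
- Six-monthly: 6/2 = 3 months, at most 6.
- Mean extra wait: 6 − 3 = 3 months.

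**Delay, if item 4 is followed.** The board looks every 6 months whether or not it meets. The mean wait is 3 months, and the extra wait is 3 − 3 = 0.

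The 3-month figure therefore measures a departure from item 4. It does not measure a defect in what the plan asks for.

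**Can both statements be kept?** Item 4 fixes how often data are reviewed, and Frequency of Meetings fixes how often the board convenes. A mid-year review needs three things:

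| Need | Where section 12 provides for it |
|---|---|
| Data | The PI's log of all adverse events and summary report (item 3); summaries and analyses on request (What is Monitored) |
| Occasion | Circulation of that summary, a teleconference (Meeting Format), or an ad hoc meeting (Frequency of Meetings) |
| Consequence | Proposed changes go to sites, a consultant if needed, then the IRBs (item 4) |

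None of these conflicts with a yearly full meeting.

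**What is not stated.** The available text gives no date for the mid-year summary, does not say that it is circulated, and does not say how the board records a review held without a meeting. The available text also breaks off partway through a sentence shortly after item 4 and resumes within the DSMB material. Wording that links the two intervals could lie in that gap, so its absence from the plan cannot be asserted.

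**The case for a change.** The best case for a change is that the text leans towards review meaning meeting. The provision for extra meetings speaks of problems arising between reviews, directly after the yearly schedule. Meeting Format places the presentation of adverse events in the open sessions of meetings, and the Communication Plan ties written findings to meetings. An auditor could then find it hard to tell whether a mid-year review had taken place.

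The other safeguards are not equivalent:
- The PI and Project Director meet twice a month and hold a fuller review every 2 months during the intervention phases, but both are internal.
- IRB renewals, with their adverse event reports, are yearly.
- Ad hoc meetings need someone to raise a concern first.
- The 1-week report to the IRB begins by asking whether an event was unexpected, so a rise in risks already listed in section 11 might not trigger it.

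There is also a mismatch of scope: item 4 covers all adverse event data, whereas the Confidentiality paragraph lists only a summary of serious events among the contents of the board's report.

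Much of this is fair as description. The mid-year review has no dated slot and no stated form of record in the available text, and the internal and IRB routes do not replace an independent look. But the argument needs the team to read the meeting schedule as cancelling an express commitment a few paragraphs earlier, and nothing in the section says that it does. Item 4 does not promise a separate written board report every six months, so requiring one would add a new standard. On scope, item 3 gives the board a summary drawn from a log of all adverse events, and What is Monitored has it review adverse event rates generally. The Confidentiality list therefore need not be read as limiting what the board sees.

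The remaining safeguards also narrow the consequence. A report form is due within 24 hours of any adverse event being identified, a steering committee meets monthly, and section 11 provides for physician referral when there are signs of low blood sugar or low blood pressure.

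**Conclusion.** The mismatch in intervals is real: two reviews a year are committed, one meeting is scheduled, and half of the reviews have no meeting attached. It is not a contradiction, because a review need not be a meeting and section 12 supplies the data, the possible occasions and the onward path for a mid-year review. A team that follows item 4 as written gives the board its six-monthly look with no added delay. The mean extra wait of 3 months arises only if item 4 is set aside, and it also rests on an assumed uniform time of onset.

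What remains is an unstated working detail: when the mid-year summary goes out and how the board notes its conclusion. A PI and board chair would ordinarily settle this between them. The plan describes the risk as likely low, the board sees cumulative data so that no event is lost to it, and no analysis depends on the point.

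The conclusion rests on two premises: that item 4 is carried out as stated, and that the unavailable DSMB text does not restrict the board to its yearly meeting. On those premises no change to the plan is needed.

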Conflict of Interest: DSMB members will be asked to disclose any conflicts of interest prior to DSMB meetings. No DSMB members will have any role on the study.

Charge of the Board: During the trial, the DSMB will assess the performance of overall study operations and any other relevant issues, as necessary. Specific items that will be reviewed by the DSMB include:

- Interim/cumulative data for evidence of study-related adverse events
- Data quality, completeness, and timeliness
- Adequacy of compliance with goals for recruitment and retention, including those related to the participation of women and minorities
- Adherence to the protocol

- Factors that might affect the study outcome or compromise the confidentiality of the trial data (such as protocol violations, unmasking, etc.)
- Interim analysis

Meeting Format: The meetings may include both open and closed sessions. In the open sessions, the PI and the Project Director presents and discusses information with the DSMB on study progress and adverse events. In closed sessions, the DSMB chairperson leads the meeting with the board members and without participation of the PI or study investigators to discuss any concerns with the progress of the study or with risks to participants. The need for closed meetings is at the discretion of the DSMB chair. Meetings may be conducted by teleconference at the request of Board members.

Frequency of Meetings: The first DSMB meeting will take place before the enrollment of the first participant in the effectiveness study. During the first DSMB meeting, a chair for the board will be selected. Then, the DSMB will meet once a year until the completion of the study. Additional meetings will be convened quickly if problems arise that require addressing between reviews. Ad hoc DSMB meetings may be requested by DSMB members, the Project Officer (PO), Columbia University IRB, or Principal Investigator (PI) at any time to discuss safety concerns.

What is Monitored: The DSMB will evaluate the progress of the trial, recruitment rates, retention rates, adverse events, unanticipated problems, and other factors affecting safety or outcomes. The DSMB will review rates of adverse events in the study (in an unblinded manner if they wish) to evaluate any changes in participant risk. The PI, Project Director, and study statistician ([name]) will be available to the DSMB to provide summary data on recruitment, data quality, adverse events, and will provide requested data analyses. The DSMB also will review major proposed modifications to the study prior to their implementation.

Confidentiality: The DSMB will not have access to personally identifiable information of participants. DSMB members agree not to disclose the results of the data except as agreed by the PI. The report to the DSMB includes actual vs. projected recruitment rates (number screened, consents, randomized, etc.), summary of serious adverse events, and any modifications to the protocol.

Communication Plan: At the end of each DSMB meeting, the chair will provide the study leadership with written information concerning findings for the trial as a whole and any relevant recommendations related to continuing, changing, or terminating the trial. The chair will prepare a summary of the meeting along with any recommendations for changes to the protocol based on the meeting. The draft report will be reviewed and edited by all Board members prior to issuing the final report. This report will not include confidential information. The report should indicate whether the study should continue as originally designed, whether the study should be modified to protect patient safety or whether the study should be terminated. The PI will send the report to the Columbia University IRB, other study site's IRBs, and to the sponsoring NIH Institute.

13. Potential Benefits

The potential benefits to participants are direct (improved health and wellness) and indirect (helping to refine the appropriateness and promote the use of a promising group-based healthy lifestyle intervention). The study will test the effectiveness of Peer GLB to improve the physical health of culturally diverse consumers with serious mental illness who are overweight or obese receiving services at supportive housing agencies.

14. Alternatives

The alternative for participants is not to participate in this study and to receive the usual care services at their supportive housing agencies (e.g., case management, wellness groups).

15. Research at External Sites

We have identified two supportive housing agencies that are participating in the project: [REDACTED] [REDACTED]. The site at [REDACTED] will be at [REDACTED] [REDACTED]. The second site is [REDACTED] in Philadelphia, PA. [REDACTED] does not have an IRB and does not require IRB review, but the Philadelphia Department of Public Health IRB has already approved the protocol locally and has approved [REDACTED] IAA request for the existing protocol.

In conjunction with the CU Morningside IRB, we have also obtained IRB approval from the City of Philadelphia Department of Public Health (PDPH) IRB (which requires review of studies involving consumers receiving services funded by PDPH, as is the case at [REDACTED]). [REDACTED] have obtained an IRB Authorization Agreement with the City of Philadelphia's Department of Public Health IRB so the PDPH IRB serves as the IRB of record for [REDACTED]

[REDACTED] does not have an IRB, and so we are requesting that the CU IRB consider entering into an IRB Authorization Agreement (IAA) so that the CU IRB can serve as the IRB of record for [REDACTED].

16. Columbia as Lead Institution

Not Applicable
